#### 4.2 Exploratory Endpoints

The following categories of exploratory endpoints will be evaluated:

- Change in ALSFRS-R domain scores
- Change in strength: HHD global percentage, HHD0, and HHD0^2,
- Change in quantitative voice characteristics as measured by Aural Analytics: maximum phonation time, pause rate, breathy vocal quality, pitch instability, regulation of voicing, articulatory precision, speaking rate, articulation rate, and monotonicity,
- Change in biofluid biomarkers of neurodegeneration and neuromuscular degeneration: serum creatinine and serum and cerebrospinal fluid (CSF) neurofilament light chain (NfL),
- Change in patient-reported outcomes: ALSAQ-40 physical mobility, independence in activities of daily living, eating and drinking, communications, and emotional reactions domain scores and ALSAQ-40 symptom index, CNS-BFS total score,
- Change in plasma concentrations of verdiperstat,
- Change in verdiperstat PD biomarkers: myeloperoxidase protein, total activity, and concentration-specific activity,
- Change in respiratory function as assessed by home spirometry, and
- Time to clinical events: first hospitalization due to a serious adverse event (SAE), first hospitalization due to an ALS-related SAE, first use of assisted ventilation, first placement of a feeding tube, first time reaching King's stage 4a or 4b, and first instance of any of the following events: hospitalization for an SAE, feeding tube placement, tracheostomy, initiation of permanent assisted ventilation (PAV), or death.

# 4.3 Safety Endpoints

In addition to the safety endpoints described in the M-SAP, the following RGB regimen-specific safety endpoint will be evaluated:

• Thyroid function: Proportion of participants with TSH ≥10 mIU/L, proportion of participants with signs or symptoms of hypothyroidism, and levels of free T3, free T4, and TSH.

#### 5. Measurement Definitions

#### 5.1 ALSFRS-R

The definitions of ALSFRS-R scores are the same as described in the M-SAP. Pre-baseline slope in ALSFRS-R (delta-FRS) is defined as 48 minus the baseline ALSFRS-R total score then divided by the number of months from onset of symptomatic weakness to the Baseline Visit. The number of months will be calculated as the difference in days from onset of symptomatic weakness to the Baseline Visit multiplied by 12 / 365.25. The date of onset of symptomatic weakness will be imputed as the fifteenth day of a month if not specified more precisely.

ALSFRS-R domain scores are exploratory measures of the primary efficacy endpoint ALSFRS-R total score.

#### **5.2** SVC

The derivation of SVC percent-predicted of normal is the same as described in the M-SAP with age calculated as number of days from date of birth to the date of a given SVC assessment divided by 365.25 and with the following correspondence between self-identified race and race defined by Global Lung Initiative (GLI) classification:

Self-identified Race	GLI-defined Race
American Indian or Alaska Native	Mixed/Other
Asian	South East Asian
Black or African American	African American
Native Hawaiian or Other Pacific Islander	Mixed/Other
White	Caucasian
Unknown	Caucasian
Not reported	Caucasian
More than one race indicated	Mixed/Other

### **5.3** Home Spirometry

Home spirometry assesses FVC remotely using a smartphone app (ZEPHYRx, Albany, NY) and a handheld spirometer (Spirobank Smart, Medical International Research, Rome, Italy). Coordinators guide participants through 3 to 8 maneuvers with live-video coaching using the ZEPHYRx platform. Flow loops are classified for acceptability and repeatability using American Thoracic Society (ATS) criteria and are manually reviewed by the NEALS Outcomes Center (Barrow Neurological Institute, Phoenix, AZ). The maximum FVC accepted by the NEALS Outcomes Center is converted to percent of predicted normal using GLI norms based on sex, age at time of assessment, height at time of screening, and race. Age is calculated as number of days from date of birth to the date of a given home spirometry assessment divided by 365.25. Higher values indicate greater respiratory function.

### 5.4 HHD and Grip Strength

The derivation of HHD upper and lower extremity scores and HHD0 are the same as described in the M-SAP with the revision that HHD0 is a composite endpoint with death or death equivalent, whichever occurs first.

Page 17 of 18

A second HHD time-to-event endpoint is defined as the time from the Baseline Visit to the second post-baseline occurrence of a muscle with a strength recording of 0 among those muscles that were non-zero at baseline or time to death or death equivalent, whichever occurs first  $(HHD0^2)$ .

Time at risk for HHD0 and HHD $0^2$  will be censored at the last date at an HHD assessment was performed up to the end of the Week 24 Visit window.

HHD global average percentage, HHD0, and  $HHD0^2$  are exploratory measures of the secondary endpoint HHD and grip strength.

#### 5.5 Quantitative Voice Characteristics

Voice samples will be collected using the Aural Analytics app installed on either an Android or iOS-based smartphone. At each assessment, participants perform a set of speaking tasks: reading 5 prespecified sentences, reading 5 sentences chosen at random from a large sentence bank, repeating a consonant-vowel sequence, producing a sustained phonation, and counting on a single breath. Speech analysis will be performed by Aural Analytics to derive the following quantitative voice characteristics: maximum phonation time, pause rate, breathy vocal quality, pitch instability, regulation of voicing, articulatory precision, speaking rate, articulation rate, and monotonicity. Aural Analytics will use data on quantitative voice characteristics and participant age, sex, race, height, and weight to derive a prediction of vital capacity at the Baseline Visit.

### 5.6 Biofluid Biomarkers of Neurodegeneration

Blood biomarkers of neurodegeneration, including biomarkers of neuromuscular dysfunction, will be assayed. These will include serum creatinine and serum and CSF neurofilament light chain (NfL). Serum creatinine will be assayed by the kinetic Jaffe method (test 001370, Labcorp, Burlington, NC). NfL will be assayed by single-molecule array (Simoa; Quanterix, Billerica, MA). Levels of serum and CSF NfL that are reported to be below the limit of quantitation will be imputed at the limit of quantitation. Levels of serum and CSF NfL will be log-transformed in all analyses.

#### 5.7 ALSAO-40

The description of the ALSAQ-40 instrument and item-level scores are the same as described in the M-SAP. Each of the five domains will be scored as the mean of all domain-specific items multiplied by 25 (range 0 to 100). An overall symptom index (SI) will be scored as the mean of the five domain scores. A domain score will be missing if more than 20% of the items are missing; otherwise, item non-response will be mean-imputed from other completed items from the same assessment. The ALSAQ-40 SI will be missing if any domain scores are missing. Higher scores indicate worse quality of life.

#### 5.8 CNS-BFS

The definition of CNS-BFS total score is the same as described in the M-SAP.

#### 5.9 Survival

The primary definition of survival time is the same as described in the M-SAP with the clarification that PAV is defined as more than 22 hours per day of noninvasive or invasive

mechanical ventilation for more than seven consecutive days. The date of PAV initiation, where applicable, will be imputed as the fifteenth day of a month if not specified more precisely. A secondary survival endpoint of death alone, independent of any death equivalent, is also defined.

Time at risk for the composite endpoint of death or death equivalent and time at risk for the endpoint of death alone will be measured from each participant's Baseline Visit. Time at risk will be censored at two time points: (1) at the Week 24 Visit as defined in the M-SAP, and (2) at a subsequent assessment of death or death equivalent scheduled approximately at the end of placebo-controlled follow-up of the last RGB participant. The primary analysis of survival will evaluate PAV-free survival to the Week 24 Visit time point.

# 5.10 King's ALS Clinical Staging System

The King's ALS Clinical Staging System (Roche et al. 2012) is a 4-level ordinal scale with the first three levels indicating the number (1, 2, or 3) of distinct central nervous system regions (bulbar, upper limb, and lower limb) with neuromuscular dysfunction and levels 4a and 4b indicating nutritional or respiratory failure secondary to ALS, respectively.

Participants will be classified to King's stage 1, 2, 3, 4a, or 4b based on scores from ALSFRS-R assessments according to a published derivation (Balendra et al. 2014). Bulbar involvement is defined as a score less than 4 on any of the ALSFRS-R questions in the bulbar domain (questions 1, 2, and 3). Upper limb involvement is defined as a score less than 4 on either of the ALSFRS-R questions related to hand function (questions 4 and 5A). Lower limb involvement is defined as a score less than 4 on the ALSFRS-R question about walking (question 8). Nutritional failure is defined as responding that the participant uses gastrostomy for greater than 50% of their nutrition. Respiratory failure is defined as a score of 0 on the ALSFRS-R question addressing dyspnea (question 10 or R-1) or a score less than 4 on the ALSFRS-R question about use of mechanical ventilation (question 12 or R-3). Participants without evidence by ALSFRS-R scores of involvement of any of the three central nervous system regions will be scored as King's stage 1 due to their confirmed diagnosis with ALS. Participant may meet criteria for both King's stage 4a and 4b.

#### 5.11 Hospitalization and Other Clinical Events

Times to the following clinically relevant events are defined:

- Time to first hospitalization due to a serious adverse event (SAE),
- Time to first hospitalization due to an ALS-related SAE,
- Time to first use of assisted ventilation,
- Time to first placement of a feeding tube,
- Time to King's stage 4a or 4b, and
- Time to first instance of hospitalization for an SAE, feeding tube placement, tracheostomy, initiation of PAV, or death.

Time at risk for each event will be measured from each participant's Baseline Visit. Time to first hospitalization excludes hospitalizations for elective procedures. ALS-related SAEs are those indicated as related to ALS disease progression by the site investigator. Participants who are already using assisted ventilation or have a feeding tube at the time of the Baseline Visit will be

excluded from analysis of those endpoints. Death or death equivalent will be considered an outcome for each of the events listed, forming a composite endpoint.

Time at risk for these events will be censored at the Week 24 Visit, if completed, the date of consent withdrawal, if withdrawn, or the last date at which the status of each endpoint is known prior to the end of the Week 24 Visit window for participants lost to follow-up. Time to King's stage 4a or 4b is interval censored between ALSFRS-R assessments.

### 5.12 Pharmacodynamic Biomarkers

Myeloperoxidase protein and activity levels in plasma samples collected at Baseline and Weeks 4, 8, 16, and 24 will be assayed among participants randomized to active treatment. Details of the assay techniques will be specified when known.

### **5.13 Clinical Safety Laboratory Tests**

Clinical safety labs include hematology, blood chemistry panel, liver function tests, thyroid function, urinalysis, and pregnancy testing in women of childbearing potential as specified in Section 9.1.2 Clinical Safety Laboratory Tests of the Master Protocol:

- Hematology: hematocrit, hemoglobin, platelet count, red blood cell (RBC) count, mean
  corpuscular volume, mean corpuscular hemoglobin, mean corpuscular hemoglobin
  concentration, RBC distribution width (RDW), RBC morphology, white blood cell (WBC)
  count, and counts and percentages of basophils, eosinophils, lymphocytes, monocytes, and
  neutrophils;
- Blood chemistry panel: bicarbonate, chloride, potassium, sodium, calcium, magnesium, phosphate, blood urea nitrogen, creatinine, estimated glomerular filtration rate (eGFR) calculated using the Modification of Diet in Renal Disease (MDRD) four-variable equation, creatinine clearance calculated using the Cockcroft-Gault equation, and glucose;
- Liver function tests: alanine aminotransferase (ALT [SGPT]), aspartate aminotransferase (AST [SGOT]), alkaline phosphatase (ALP), albumin, total protein, total bilirubin (TBL);
- Thyroid function tests: thyroid-stimulating hormone (TSH), reflex T3 and T4 when TSH levels are abnormal;
- Urinalysis: clarity, color, specific gravity, pH, microalbumin, protein, glucose, ketones, bilirubin, urobilinogen, nitrite, leukocyte esterase, and blood; and
- Pregnancy: qualitative and quantitative serum human chorionic gonadotropin (hCG).

Clinical safety labs will also include derived measures of potential drug-induced liver injury (DILI), including those that potentially meet the Hy's law criteria, as distinct safety lab outcomes.

Three potential DILI criteria will be defined:

- ALT or AST >3x ULN with TBL >1.5x ULN
- AST or ALT >3x ULN with TBL >2x ULN
- AST or ALT >3x ULN with TBL >2x ULN and ALP <2x ULN (potential Hy's Law cases) where ULN is upper level of normal and all levels are measured on the same day.

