| ALS & Medical History | Master | X | | | | | | | | | | |
| Demographics | Master | X | | | | | | | | | | |
| Physical Examination | Master | X | | | | | | | | | | |
| Neurological Exam | Master | X | | | | | | | | | | |
| Vital Signs ⁷ | Master | X | | X | X | X | | X | | X | | |
| Slow Vital Capacity | Master | X ²⁰ | | X | | X | | X | | X | | |
| Home Spirometry | Regimen | X ²⁰ | | X | | X | | X | | X | | |
| Muscle Strength Assessment | Master | | | X | | X | | X | | X | | |
| ALSFRS-R | Master | X | | X | X | X | X | X | X | X | X | |
| ALSAQ-40 | Regimen | | | X | | | | | | | X | |
| CNS bulbar Function Scale | Regimen | | | X | | X | | X | | | X | |
| 12-Lead ECG | Regimen | X | | | | X | | | | | X | |

HEALEY ALS Platform Trial
 Regimen-Specific Appendix B, Verdiperstat
 Version 6.0 , 02-December-2021
 CONFIDENTIAL

| Activity | Master Protocol or Regimen-Specific | Master Protocol Screening ¹ | Regimen Specific Screening ¹ | Baseline | Week 2 ² | Week 4 ^{18,19} | Week 8 ^{18,19} | Week 12 | Week 16 ^{18,19} | Week 20 | Week 24 or Early Term. Visit ^{3, 18} | Follow-up Safety Call ^{3,4} |
|--|-------------------------------------|--|---|-----------------|---------------------|-------------------------|-------------------------|----------------|--------------------------|-----------------|---|--------------------------------------|
| | | Clinic | Clinic | Clinic | Phone | Clinic | Clinic | Phone | Clinic | Phone | Clinic | Phone |
| | | -42 to -1 Days | -41 to 0 Days | Day 0 | Day 14 \pm 3 | Day 28 \pm 7 | Day 56 \pm 7 | Day 84 \pm 3 | Day 112 \pm 7 | Day 140 \pm 3 | Day 168 \pm 7 | 28 \pm 7 days after last dose |
| Clinical Safety Labs ⁸ | Master | X | | X | | X | X | | X | | X | |
| Verdiperstat (BHV-3241) specific PD biomarkers ¹⁰ | Regimen | | | X | | X | X | | X | | X | |
| PK Blood Collection ¹⁰ | Regimen | | | X | | X | X | | X | | X | |
| Biomarker Blood Collection | Master | | | X | | | X | | X | | X | |
| Biomarker Urine Collection | Master | | | X | | | X | | X | | X | |
| DNA Collection ¹¹ (optional) | Master | | | X | | | | | | | | |
| CSF Collection (optional) | Master | | | X | | | | | X ¹⁷ | | | |
| Concomitant Medication Review | Master | X | X | X | | X | X | X | X | X | X | |
| Concomitant Medication Review | Regimen | | | | X | | | | | | | |
| Adverse Event Review ⁹ | Master | X | X | X | X | X | X | X | X | X | X | X |
| Columbia-Suicide Severity Rating Scale | Master | | | X | | X | X | | X | | X | |

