5.9.1.4 Liver

Minimally non-adverse, increased alanine aminotransferase and slight (adaptive) histopathological effects in the liver were observed in rats during the preclinical studies; these are likely related to enzyme induction (e.g., CYP2B1 induction). In the MAD study [18], several participants, including those receiving verdiperstat and placebo, had increases in hepatic transaminases.

In the ongoing, blinded Phase 3 study in subjects with MSA (BHV3241-301), preliminary data indicate that 4 subjects (1.2%) discontinued the study due to elevations in liver enzymes. Of these, 3 subjects had elevations 5x upper limit of normal. All 4 subjects were asymptomatic, and the elevations in liver enzymes were isolated without increased bilirubin levels. Elevated levels returned to normal in a few weeks.

In aggregate, the clinical data show a possible association of asymptomatic and reversible liver enzyme increases with verdiperstat. The present study will involve monitoring of liver function tests.

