# 6.6.2 Safety Labs

Summaries and analyses of clinical safety labs are the same as specified in the M-SAP with the revision that lab results collected more than 28 days after last dose of study drug will not be tabulated, that abnormal levels will be classified to a toxicity grade based on quantitative grading using National Cancer Institute (NCI) Common Terminology Criteria for Adverse Events (CTCAE) version 5.0, and with the addition that maximum toxicity over all post-baseline visits that occur within 28 days or fewer after last dose of study drug will be included in shift tables along with visit-specific shifts.

The proportion of participants with TSH ≥10 mIU/L and the proportion with signs or symptoms of hypothyroidism will be presented as shift tables vs. the status of each participant at baseline for each visit and over all post-baseline visits that occur within 28 days or fewer after last dose of study drug by treatment group in all safety samples. The absolute level and the absolute change from baseline for free T3, free T4, and TSH will be summarized as means, standard deviations, medians, and ranges at each visit by treatment group in all safety samples.

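### The three liver-injury flags need every value on one day, so a participant whose ALT/AST is back to 3x ULN or below before bilirubin crosses its threshold is not flagged

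*SAP*

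**What the plan says.** SAP 5.13 makes the DILI measures safety-lab outcomes in their own right. The first criterion is "ALT or AST >3x ULN with TBL >1.5x ULN". The second is "AST or ALT >3x ULN with TBL >2x ULN". The third adds ALP below 2x ULN to the second and is the potential Hy's Law criterion. After the third bullet comes "where ULN is upper level of normal and all levels are measured on the same day". That clause also defines ULN, which all three bullets use, so the natural reading is that it governs all three, although its position leaves this to inference. Neither the SAP nor the regimen appendix (RSA) gives a time window linking a transaminase value to a bilirubin value.

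SAP 6.6.2 adds that "lab results collected more than 28 days after last dose of study drug will not be tabulated". It also puts each participant's worst toxicity grade across post-baseline visits, within the same 28-day limit, into shift tables. Other lab summaries are left to the Master SAP.

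The RSA Schedule of Activities places safety labs at Screening, Baseline and Weeks 4, 8, 16 and 24, each post-baseline visit with a window of 7 days either side. On earlier liver findings, RSA 5.9.1.4 reports four discontinuations for raised liver enzymes in the blinded MSA study. Three of them reached 5x ULN, and none had raised bilirubin. "Elevated levels returned to normal in a few weeks".

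**The concern.** A same-day rule works when both analytes are high in one draw. It fails when they are high in sequence and the transaminase has come down before the bilirubin goes up. With draws one to two months apart, and earlier enzyme elevations described as resolving within weeks, two consecutive draws can easily fall on either side of that change.

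RSA 5.9.1.4 accepts a possible link between verdiperstat and reversible enzyme rises and relies on monitoring in this trial. The DILI flags are the only outcomes specified in these documents that combine transaminase and bilirubin within a participant. If a sequential case is not flagged, the report can show no potential Hy's Law case in an active arm of 120 when the lab record contains one that needed review.

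**Working it through.** The plan attaches no number to these criteria, so there is no figure to reproduce. The check is of the rule's logic and of the visit schedule.

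**1. The rule on constructed sequences.** Values are multiples of ULN, with ALP at 1x throughout.

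| Sequence | First draw | Second draw | Same-day rule, criteria 1/2/3 | Any-day pairing |
|---|---|---|---|---|
| A | ALT 5, TBL 1 | ALT 1.2, TBL 2.5 | no / no / no | yes / yes / yes |
| B | ALT 10, TBL 1 | ALT 4, TBL 2.5 | yes / yes / yes | yes / yes / yes |
| C | ALT 5, TBL 2.5 | ALT 1, TBL 1 | yes / yes / yes | yes / yes / yes |

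Only A changes. The rule asks for ALT/AST above 3x ULN on the bilirubin day, not for the peak on that day, so B is counted. The participant missed is the one whose ALT/AST is at or below 3x ULN in every sample with TBL over its threshold. The third criterion also needs ALP below 2x ULN in that same sample.

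**2. Spacing of scheduled draws** (RSA Schedule of Activities: Days 0, 28, 56, 112, 168; windows of 7 days after baseline).

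- Baseline to Week 4: 28 days, range 21 to 35.
- Week 4 to Week 8: 56 − 28 = 28 days, range 14 to 42.
- Week 8 to Week 16: 112 − 56 = 56 days, range 42 to 70.
- Week 16 to Week 24: 168 − 112 = 56 days, range 42 to 70.

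**3. How long ALT stays above 3x ULN.** This is an illustration under an assumption: a log-linear fall from a peak of P x ULN to 1x ULN in T days. Time above 3x ULN after the peak is T × ln(P/3) / ln(P). RSA 5.9.1.4 gives 5x ULN as a size and a few weeks as a duration; I take T as 14 to 28 days.

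- P = 5: ln(5/3)/ln(5) = 0.317, giving 4.4, 6.7 and 8.9 days for T = 14, 21 and 28.
- P = 10: ln(10/3)/ln(10) = 0.523, giving 7.3, 11.0 and 14.6 days.

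Against gaps of 28 or 56 days, ALT would usually be at or below 3x ULN by the next scheduled draw. An exception is a 10x peak with slow recovery, at the 14-day extreme between Weeks 4 and 8. Unscheduled draws or a persisting elevation would also change this.

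**4. The 28-day limit.** Take a participant who stops drug at the Week 8 or Week 16 visit and stays on study. The next scheduled draw is 42 to 70 days later. Since 42 > 28, SAP 6.6.2 excludes it from tabulation at any point in the window. An unscheduled or early-termination draw could fall inside the limit, but the same-day rule still prevents pairing it with the earlier ALT.

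**The case against.** Several points on the other side are sound and limit the claim.

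- A reader might infer that any case whose bilirubin rises after the transaminase peak is lost. The rule does not do that; sequence B is counted.
- A reader might scale the MSA experience: 4/336 = 1.2%, or 4/168 = 2.4% if all four were on active under 1:1 allocation, giving 120 × 1.2% = 1.4 to 120 × 2.4% = 2.9 participants here. That is a count of enzyme-related discontinuations, not of missed cases. RSA 5.9.1.4 says all four were without a bilirubin rise, so the evidence for a sequential case there is 0 of 4. The MSA study also runs 48 weeks with an optional 48 open-label, against 24 here.
- The data are not lost. The toxicity shift tables show each analyte separately within the 28-day limit, adverse events are listed, and the Data Safety Monitoring Board reviews benefit and risk. Nothing in the documents makes the DILI flags decisive by themselves.
- The Master SAP is not among the documents and may contain a peak-value liver display.

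What these points do not answer is the pairing. Shift tables by analyte are not specified to show that the same participant had both elevations, and the regimen SAP, which prevails over the Master SAP under its Section 1, specifies only same-day pairing.

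**Conclusion.** The point holds in this limited form: a participant whose ALT/AST has fallen to 3x ULN or below before TBL crosses its threshold meets none of the three criteria, and the draw spacing together with the 28-day limit leaves room for that to happen. This rests on reading the same-day clause as governing all three criteria. The estimate of time above 3x ULN rests on the assumed log-linear fall over 14 to 28 days; the gap in the rule does not depend on it.

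The documents do not say how often bilirubin follows the transaminases in this way, and they support no count of missed cases. It would be wrong to infer that a case has been or will be missed. This is a cheap improvement to a safety definition, not a defect that undermines the safety analysis.

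**What to change.** In SAP 5.13:

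1. Keep the three same-day flags and state that the same-day clause applies to all of them.
2. Add a per-participant flag and summary of maximum post-baseline ALT/AST (above 3x ULN) against maximum TBL (above 1.5x and above 2x ULN) on or after the ALT/AST elevation, on any day, with ALP taken on the ALT/AST date. State which ALT/AST date is the anchor; the first value above 3x ULN is the simplest choice.
3. For these flags only, include available labs later than 28 days after the last dose when the qualifying ALT/AST fell inside that limit, and note the exception in SAP 6.6.2.
4. List the ALT, AST, TBL and ALP time course, with dosing dates, for every flagged participant.

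A fixed window such as 30 days would not be enough, because no two scheduled draws from Week 8 onward are closer than 42 days.

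The cost is a few sentences and a small amount of programming on labs already collected, with no new tests and no change to participant management. The any-day pairing will produce a few false positives, such as an unrelated bilirubin rise long after the enzymes settled; the listing resolves these.
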